5.3.5.7 Hospitalization or Prolonged Hospitalization

Any adverse event that results in hospitalization (i.e., inpatient admission to a hospital) or prolonged hospitalization should be documented and reported as a serious adverse event (per the definition of serious adverse event in Section 5.2.2), except as outlined below.

An event that leads to hospitalization under the following circumstances should not be reported as an adverse event or a serious adverse event:

- Hospitalization for a preexisting condition, provided that all of the following criteria are met:
 - The hospitalization was planned prior to the study or was scheduled during the study when elective surgery became necessary because of the expected normal progression of the disease
 - The patient has not experienced an adverse event

5.3.5.8 Patient-Reported Outcome Data

Adverse event reports will not be derived from PRO data by the Sponsor. Sites are not expected to review the PRO data for adverse events.

5.4 IMMEDIATE REPORTING REQUIREMENTS FROM INVESTIGATOR TO SPONSOR

Certain events require immediate reporting to allow the Sponsor to take appropriate measures to address potential new risks in a clinical trial. The investigator must report such events to the Sponsor immediately; under no circumstances should reporting take place more than 24 hours after the investigator learns of the event. The following is a list of events that the investigator must report to the Sponsor within 24 hours after learning of the event, regardless of relationship to study drug:

- Serious adverse events (defined in Section 5.2.2; see Section 5.4.2 for details on reporting requirements)
- Pregnancies (see Section 5.4.3 for details on reporting requirements)
- Medical device complaints (see Section 5.4.4 for details on reporting requirements)

For serious adverse events, the investigator must report new significant follow-up information to the Sponsor immediately (i.e., no more than 24 hours after becoming aware of the information). New significant information includes the following:

- New signs or symptoms or a change in the diagnosis
- Significant new diagnostic test results
- Change in causality based on new information
- Change in the event's outcome, including recovery
- Additional narrative information on the clinical course of the event

Investigators must also comply with local requirements for reporting serious adverse events to the local health authority and IRB/EC.

5.4.2 Reporting Requirements for Serious Adverse Events

After informed consent has been obtained, serious adverse events will be reported from Day 1 visit of this study. For ongoing serious adverse events since the parent study, the adverse event will be reported as outlined in Section 5.1. Investigators should record all case details that can be gathered immediately (i.e., within 24 hours after learning of the event) on the Adverse Event eCRF and submit the report via the EDC system. A report will be generated and sent to Roche Safety Risk Management by the EDC system.

In the event that the EDC system is unavailable, the paper Clinical Trial Serious Adverse Event/Adverse Event of Special Interest Reporting Form provided to investigators should be completed and submitted to the Sponsor or its designee immediately (i.e., no more than 24 hours after learning of the event), either by faxing or by scanning and emailing the form using the fax number or email address provided to investigators. Once the

EDC system is available, all information will need to be entered and submitted via the EDC system.

5.4.3 Reporting Requirements for Pregnancies

5.4.3.1 Pregnancies in Female Patients

Female patients of childbearing potential will be instructed through the Informed Consent Form to immediately inform the investigator if they become pregnant during the study. A paper Clinical Trial Pregnancy Reporting Form should be completed and submitted to the Sponsor or its designee immediately (i.e., no more than 24 hours after learning of the pregnancy), either by faxing or by scanning and emailing the form using the fax number or email address provided to investigators. Pregnancy should not be recorded on the Adverse Event eCRF. The investigator should counsel the patient, discussing the risks of the pregnancy and the possible effects on the fetus. Monitoring of the patient should continue until conclusion of the pregnancy. Any serious adverse events associated with the pregnancy (e.g., an event in the fetus, an event in the mother during or after the pregnancy, or a congenital anomaly/birth defect in the child) should be reported on the Adverse Event eCRF. In addition, the investigator will submit a Clinical Trial Pregnancy Reporting Form when updated information on the course and outcome of the pregnancy becomes available.

5.4.3.2 Abortions

A spontaneous abortion should be classified as a serious adverse event (as the Sponsor considers abortions to be medically significant), recorded on the Adverse Event eCRF, and reported to the Sponsor immediately (i.e., no more than 24 hours after learning of the event; see Section [5.4.2](#)).

If a therapeutic or elective abortion was performed because of an underlying maternal or embryofetal toxicity, the toxicity should be classified as a serious adverse event, recorded on the Adverse Event eCRF, and reported to the Sponsor immediately (i.e., no more than 24 hours after learning of the event; see Section [5.4.2](#)). A therapeutic or elective abortion performed for reasons other than an underlying maternal or embryofetal toxicity is not considered an adverse event.

All abortions should be reported as pregnancy outcomes on the paper Clinical Trial Pregnancy Reporting Form.

5.4.3.3 Congenital Anomalies/Birth Defects

Any congenital anomaly/birth defect in a child born to a female patient exposed to study drug should be classified as a serious adverse event, recorded on the Adverse Event eCRF, and reported to the Sponsor immediately (i.e., no more than 24 hours after learning of the event; see Section [5.4.2](#)).

5.4.4 Reporting Requirements for Medical Device Complaints

In this study, the wearable monitor (e.g., Apple Watch) is considered a medical device. The investigator must report all medical device complaints to the Sponsor. The investigator should document as much information as possible and forward the complaints to the Sponsor immediately (i.e., no more than 24 hours after learning of the event). If the medical device results in an adverse event to the study patient, the event must be reported on the Adverse Event eCRF and submitted through the EDC system. If the event is serious, the Adverse Event eCRF must be completed immediately (i.e., no more than 24 hours after learning of the event), as outlined in Section [5.4.2](#).

For complaints and adverse events associated with the wearable monitor (e.g., Apple Watch), the Sponsor will forward the complaint to the manufacturer. The manufacturer will report all adverse events according to the regulatory requirements for reporting of medical device-related adverse events (21 CFR 803).

5.5 FOLLOW-UP OF PATIENTS AFTER ADVERSE EVENTS

5.5.1 Investigator Follow-Up

The investigator should follow each adverse event until the event has resolved to baseline grade or better, the event is assessed as stable by the investigator, the patient is lost to follow-up, or the patient withdraws consent. Every effort should be made to follow all serious adverse events considered to be related to study treatment or trial-related procedures until a final outcome can be reported.

During the adverse event reporting period (defined in Section [5.3.1](#)), resolution of adverse events (with dates) should be documented on the Adverse Event eCRF and in the patient's medical record to facilitate source data verification.

All pregnancies reported during the study should be followed until pregnancy outcome.

5.5.2 Sponsor Follow-Up

For serious adverse events and pregnancies, the Sponsor or a designee may follow up by telephone, fax, email, and/or a monitoring visit to obtain additional case details and outcome information (e.g., from hospital discharge summaries, consultant reports, autopsy reports) in order to perform an independent medical assessment of the reported case.

5.6 EXPEDITED REPORTING TO HEALTH AUTHORITIES, INVESTIGATORS, INSTITUTIONAL REVIEW BOARDS, AND ETHICS COMMITTEES

The Sponsor will promptly evaluate all serious adverse events against cumulative product experience to identify and expeditiously communicate possible new safety findings to investigators, IRBs, ECs, and applicable health authorities based on applicable legislation.

To determine reporting requirements for single adverse event cases, the Sponsor will assess the expectedness of these events through use of the reference safety information in the document listed below:

Drug	Document
AT-527	AT-527 Investigator's Brochure

The Sponsor will compare the severity of each event and the cumulative event frequency reported for the study with the severity and frequency reported in the applicable reference document.

Reporting requirements will also be based on the investigator's assessment of causality and seriousness, with allowance for upgrading by the Sponsor as needed.

An aggregate report of any clinically relevant imbalances that do not favor the test product will be submitted to health authorities.

6. STATISTICAL CONSIDERATIONS AND ANALYSIS PLAN

The final analysis of the study will occur at the end of the study (see Section 3.2).

Differential loss to follow-up may introduce bias into the study. Patients may be lost to follow-up because they are fully recovered or they experience an adverse outcome.

Details of the statistical analysis methods and endpoints will be described in the study Statistical Analysis Plan (SAP) which will be finalized prior to study completion.

6.1 DETERMINATION OF SAMPLE SIZE

This study is observational in nature and designed for estimation and hypothesis-generating purposes. The sample size of approximately 1040 patients is based on site feasibility assessment rather than statistical considerations.

6.2 SUMMARIES OF CONDUCT OF STUDY

Patient disposition (i.e., the number of patients who enroll, discontinue, or complete the study) will be summarized descriptively. Reasons for premature study discontinuation will also be summarized and may be listed if appropriate. Enrollment and major protocol deviations will be listed and evaluated for their potential effects on the interpretation of study results.

A patient disposition figure will show the flow of patients starting with the parent study and finishing with the number of patients contributing data to this study.

6.3 SUMMARIES OF DEMOGRAPHIC AND BASELINE CHARACTERISTICS

Demographic and baseline characteristics (including age, sex, race/ethnicity, region, treatment group in the parent study, RT-PCR status, seropositive status, presence of

risk factors, preexisting symptoms and other patient characteristics of interest) will be summarized using descriptive statistics including means, standard deviations, medians, and ranges for continuous variables and proportions for categorical variables, as appropriate. Summaries will be presented overall. Demographic and baseline characteristics may be obtained from data collected in the parent study.

Patient characteristics will be displayed in a tabular format (number and percentage), including demographics, medical history before COVID-19, and treatments received for COVID-19.

To evaluate the potential for selection bias, patient characteristics will be compared between the parent study and the follow-up study to examine for systematic differences.

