3. STUDY DESIGN

3.1 DESCRIPTION OF THE STUDY

This is a Phase III, non-treatment, observational, multicenter, follow-up study to assess long-term outcomes for approximately 6 months in patients diagnosed with COVID-19 who previously enrolled a RO7496998 (AT-527) study, also referred to as the parent study.

There is no study drug or other treatment required in this follow-up study. Throughout this protocol, “study drug” refers to treatment administered in the parent study prior to this study (CV43140).

Any patients previously enrolled in a Phase III RO7496998 (AT-527) study will be informed of the opportunity to participate in this study (CV43140). An attempt will be made, where possible, to consent patients to this study at the same time patients are consented to the parent study. At the latest, patients must provide consent at the Day 1 visit (baseline) of this study (CV43140), prior to the first assessment.

The Day 1 visit (baseline) can coincide with the final visit of the parent study, or as soon as possible after the final visit and within 7 days. Study outcomes will be assessed by measuring specific endpoints in patients at either daily (i.e., continuous measurements via consumer-grade wearable devices), weekly, or monthly time intervals for approximately 6 months. Patients will complete the COVID-19 Symptom Diary and Patient Global Impression of Severity (PGIS) every week; Patient Reported Outcomes Measurement Information System (PROMIS)-Dyspnea Questionnaire, St. George's Respiratory Questionnaire (SGRQ), and EuroQol 5-Dimension, 5-Level Questionnaire (EQ-5D-5L) every month; Work Productivity and Activity Impairment Questionnaire plus Classroom Impairment Questions: Specific Health Problems (WPAI+CIQ: SHP) at the Day 1 visit, Months 3 and 6.

Patients will be assessed through concomitant medication, NP swabs (as clinically indicated), blood samples, and urine samples (see [Appendix 1](#) for details regarding the timing of these assessments). Patients will be closely monitored for COVID-19 signs and symptoms and adverse events; adverse events will be graded according to National Cancer Institute Common Terminology Criteria for Adverse Events (NCI CTCAE) v5.0. Patients will be assessed monthly for COVID-19-related medically-attended visits.

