4.1.1 Inclusion Criteria

Patients must meet the following criteria for study entry:

- Signed Informed Consent Form (signed by patient's legally authorized representative for patients who have not attained the age of majority)
- Signed Assent Form when appropriate, as determined by patient's age, individual site, and country standards
- Age ≥ 18 years (regardless of weight) at the time of signing Informed Consent Form or age ≥ 12 to < 18 years (weight ≥ 40 kg) at the time of signing Informed Consent Form (and Assent Form)
- Ability, judged by the investigator, to comply with the study protocol
- Patient was diagnosed with COVID-19 and enrolled in a Phase III RO7496998 (AT-527) COVID-19 study.

Note: Patients who completed all study assessments in the parent study are eligible, regardless of whether patients completed or discontinued early from the study drug.

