4.1.2 Exclusion Criteria

Patients who meet any of the following criteria will be excluded from study entry:

- Participation in an interventional study at the time of enrollment or plans to enroll in an interventional study during this study
- Any serious medical condition or abnormality of clinical laboratory tests that, in the investigator's judgment, precludes the patient's safe participation in and completion of the study

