4.2 METHOD OF TREATMENT ASSIGNMENT AND BLINDING

This is a non-randomized, observational, and non-treatment study. After initial written informed consent has been obtained, all screening procedures and assessments have been completed, and eligibility has been established for a patient, the study site will set up the patient in the electronic data capture (EDC) system with the same patient identification number as from the parent study.

The treatment arm to which patients were assigned in the parent study will not be disclosed until the final analysis of the parent study is reported, which may occur during this study (CV43140).

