6.4 STATISTICAL ANALYSES

The analysis population will consist of all patients enrolled in the study. Long-term clinical and PROs will be summarized descriptively and trends over time will be explored. Outcomes may also be explored by patient characteristics (e.g., treatment received in the parent study), as appropriate.

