6.5 SAFETY ANALYSES

The safety analyses will include all enrolled patients in the study.

Safety will be assessed through descriptive summaries of serious adverse events (nature, frequency, and severity) and vital signs. Serious adverse events will also be listed. Safety may be explored by study treatment received in the parent study, as appropriate.

All verbatim adverse event terms will be mapped to Medical Dictionary for Regulatory Activities thesaurus terms, and adverse event severity will be graded according to NCI CTCAE v5.0. All adverse events, including serious adverse events that are continuing/persisting from the parent study (regardless of causal association with the study drug administered in the parent study) or any new adverse event with an onset date on or after the first day of enrollment and during this follow-up study, will be summarized by mapped term, appropriate thesaurus level, and severity grade. For events of varying severity, the highest grade will be used in the summaries. Deaths and cause of death will be summarized.

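### Does the selection check in Section 6.3 fail because it could hide selection that differs by parent treatment arm?

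*Combined protocol and SAP*

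**What the plan says.** Section 6.3 states the purpose of the check and then the check itself: "patient characteristics will be compared between the parent study and the follow-up study to examine for systematic differences". The parent column could be all parent patients, those who completed the parent assessments, or those who did not roll over; the text does not say. Baseline summaries are to be shown overall. Parent treatment group is one of the listed characteristics, and Section 6.2 plans a disposition figure that starts from the parent study.

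Results by parent treatment are optional. Section 6.4 says: "Outcomes may also be explored by patient characteristics (e.g., treatment received in the parent study), as appropriate". Section 6.5 says: "Safety may be explored by study treatment received in the parent study, as appropriate". Section 6.4.1 rules out a formal test of the primary endpoint, and Sections 6.4.2 and 6.4.3 rule out p-values for the other endpoints.

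Entry depends partly on events after parent treatment. The note in Section 4.1.1 reads "Patients who completed all study assessments in the parent study are eligible", and Section 4.1.2 excludes patients, at the investigator's judgement, for "Any serious medical condition or abnormality of clinical laboratory tests that" makes participation unsafe. Section 3.1 aims, where possible, to "consent patients to this study at the same time patients are consented to the parent study". Under Section 4.2 each patient is set up "with the same patient identification number as from the parent study", and the parent arm "will not be disclosed until the final analysis of the parent study is reported". Section 6 leaves the detail of methods to a SAP; the file reviewed contains only the protocol text.

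**The concern.** The follow-up cohort is a subset of the parent study. If the parent column is the whole parent study, enrolled patients stand on both sides of the comparison and any difference shrinks. With high rollover the check could look reassuring while the patients left behind are quite different.

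The arms are also pooled. If sicker patients drop out of one arm and healthier patients out of the other, the two effects can cancel in the pooled table. A later display of symptoms or adverse events by parent treatment would then compare groups that randomisation no longer balances, and the planned check would give no warning. This could happen with the arm undisclosed, because completion of parent assessments and serious illness may themselves depend on treatment.

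**Working it through.** The plan has no figure to reproduce. The 1040 in Section 6.1 is a feasibility number with no alpha, power or effect size. The rollover fraction f, the number and ratio of arms, and the prevalence of any characteristic are not given, so all are assumed below.

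**Overlap.** Let E, N and P be the proportion with a characteristic among enrolled, non-enrolled and all parent patients. Then P = fE + (1−f)N, so E − P = (1−f)(E − N). A true 10-point gap between enrolled and non-enrolled shows as 5, 3, 2 or 1 points at f = 0.5, 0.7, 0.8 or 0.9. This rescaling can be undone for means and proportions: with P = 10%, E = 12% and f = 0.8, N = (10 − 0.8 × 12)/0.2 = 2%. Medians and ranges cannot be recovered this way. E − P is also exactly the shift of the enrolled group away from the parent population, which is the bias that concerns an overall descriptive summary.

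**Two arms.** Assume equal arms, the same f and the same prevalence in each parent arm. Let dA and dB be enrolled minus non-enrolled within arm, in points. Then:

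- pooled check = (1−f)(dA + dB)/2
- gap between arms among the enrolled = (1−f)(dA − dB)

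With 10% prevalence, at f = 0.8 (f = 0.5; f = 0.9):

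| dA, dB | Pooled check | Arm gap among enrolled |
|---|---|---|
| +10, +10 | 2.0 (5.0; 1.0) | 0 |
| +10, 0 | 1.0 (2.5; 0.5) | 2.0 (5.0; 1.0) |
| +10, −5 | 0.5 (1.25; 0.25) | 3.0 (7.5; 1.5) |
| +10, −10 | 0.0 (0.0; 0.0) | 4.0 (10.0; 2.0) |

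The check depends on the sum of dA and dB and the gap on their difference, so neither predicts the other. At f = 0.8, (+5, +5) gives a check of 1.0 and a gap of 0, while (+20, 0) gives 2.0 and 4.0. The last pair needs a commoner characteristic, for example 40%: 0.8 × 44 + 0.2 × 24 = 40.

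**Which step does the masking?** Take the last table row at f = 0.8. Enrolled patients are at 12% and 8%, which pool to 10%. Non-enrolled patients are at 2% and 18%, which also pool to 10%. The pooled difference is 0.0 against the whole parent study and 0.0 against the non-enrolled. The cause is pooling, not overlap.

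A second set of inputs agrees (40% prevalence, equal arms, opposite selection). Both pooled comparisons give 0.0, with arm gaps of 12.8, 9.1 and 4.4 points at f = 0.5, 0.7 and 0.9. At f = 0.7 the within-arm figures are ±4.6 points against the parent arm and ±15.2 against the non-enrolled, so a split by arm reveals the pattern with either comparator. If selection occurs in one arm only at f = 0.7, the pooled check shows 2.3 points against 4.6 in the affected arm.

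**Scale.** With 520 enrolled per arm, the 95% chance half-width for 12% versus 8% is 1.96 × √[(0.12 × 0.88 + 0.08 × 0.92)/520] = 3.6 points. The 4.0-point gap at f = 0.8 is slightly above this and the 2.0-point gap at f = 0.9 is below it. For the f = 0.5 extreme (15% versus 5%) the half-width is 1.96 × √[(0.15 × 0.85 + 0.05 × 0.95)/520] = 3.6, and the 10.0-point gap clearly exceeds it.

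**What an added non-enrolled table could show.** Non-enrolled = 1040/f − 1040 = 1040, 446, 260 or 116 at f = 0.5, 0.7, 0.8 or 0.9, so 520, 223, 130 or 58 per arm. The half-width of a 10% proportion per arm, 1.96 × √(0.09/n), is 2.6, 3.9, 5.2 or 7.7 points. The table is least precise where overlap shrinks the difference most.

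**The case for a change.** The strongest case for a change is that the check is the plan's stated tool against selection bias, yet its comparator is undefined. A whole-parent column may include patients who could not enter, and f has no fixed denominator until the column is settled. By-treatment results are optional but foreseeable. Section 6.8 anticipates a subgroup by completion of AT-527, Section 6.7 allows interim safety analyses for a marketing application, and Section 5.6 promises health authorities an aggregate report of imbalances unfavourable to the test product. Undisclosed arms and early consent reduce arm-specific selection but cannot exclude it. Most of the characteristics named in Section 6.3 precede treatment, whereas selection by arm would more likely act through status at the end of the parent study. The remedy is a paragraph and a few tables.

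Much of this stands as description. The column is undefined, no split by arm is stated, and at f = 0.5 the arm gaps could be material. It does not show that following the plan misleads. The primary summary is unaffected, and unequal rollover by arm would be visible because treatment group is itself a listed characteristic. The means to go further are already there: the shared patient number, the planned use of parent data, and disclosure of the arm once the parent study's final analysis is reported. An always-on pooled comparison with non-enrolled patients would not cure the masking, and for means and proportions it repeats what the two planned columns already yield.

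**Conclusion.** No change to the plan is needed. What remains is missing detail of a kind that belongs in the SAP and that a competent analyst would supply: say who forms the parent column and, if outcomes or safety are shown by parent treatment, repeat the check within arm after disclosure. The comparison as written suits the descriptive primary objective.

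Under the assumptions above (two equal arms, 10% prevalence), the hidden arm gap in the exactly opposite case is 10.0, 4.0 or 2.0 points at f = 0.5, 0.8 or 0.9, against a chance half-width of about 3.6. Nothing in the documents suggests opposite selection by arm, and nothing fixes f, so these figures bound an illustration and do not estimate a bias in this study. If rollover proved low and by-treatment results became prominent, the within-arm table would deserve more weight when those results are read.
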